
Purpose and Study Rationale
 
Chronic pain affects at least 10% of the global population but is often poorly managed, given the variable efficacy of available pharmacological treatments and the limited accessibility of multidisciplinary interventions. The legalization of cannabis in at least 14 countries and the increasing regulatory approval of cannabis preparations and synthetic cannabinoids and analogues have led to a growing interest in the use of medical cannabis products to manage chronic pain. This use is supported by research demonstrating important interactions between cannabinoids and the human endocannabinoid system and pain modulation pathways. While medical cannabis products are increasingly available to practitioners who treat pain, there is little evidence-based guidance for prescribing or titrating these treatments to manage chronic non-cancer pain. This prospective registry aims to assemble real-world data regarding the use of Spectrum Therapeutics (ST) medical cannabis products in subjects with chronic non-cancer pain in countries where these products are commercially available. The registry will also assess treatment outcomes, including pain and related symptoms, global impressions of improvement, and change in concomitant pain medications (opioid use in particular), to better inform the utility of ST products for chronic non-cancer pain management.
	

Study Objectives

Primary Objective:

- To describe patterns of physician selection of Spectrum Therapeutics (ST) medical cannabis treatment regimen, expressed as average daily dose of THC and CBD (in mg), and mode of administration (ingested or inhaled), in the management of chronic non-cancer pain in countries where these products are commercially available.

Secondary Objectives:

- To describe subject product and dose adjustment (under medical follow-up) over time.
- To assess outcomes of treatment, including pain relief and effects on sleep, daily functioning, and quality of life.
- To assess global impressions of treatment effectiveness as reported by subjects and physicians.
- To assess changes in daily dose of opioids, other medications over time.

Safety Objective:

- To assess the safety and tolerability of ST products in subjects with chronic pain.

Study Design

The present study is a prospective, observational registry designed to generate real-world data on the physician-recommended use of ST products for the management of chronic non-cancer pain in countries where these products are commercially available. The study will enroll 1500 subjects from 50-150 sites in geographic regions of ST product distribution, over a 2-year period. Subjects at each site will be followed for one year to collect data on demographics, chronic pain classification, cannabis experience, treatment goals, concomitant medication(s), ST treatment regimen, clinical assessment, subject-reported outcomes, and safety.

The study includes five physician-verified visits (baseline, 2, 4, 8, and 12 months), and four at-home subject-verified follow-ups (months 1, 3, 6, 10). Physician verified follow-ups can be conducted in person or via telemedicine. Additionally, should there be a need, according to the physician's judgement, there may be other unscheduled visits, either in-clinic, or via telemedicine.

All data will be collected using *REDCap Cloud* data management platform, via online electronic case report forms (eCRFs), and questionnaires. During physician-verified visits, online questionnaires will be completed by both the physician and the subject (in the presence of a physician or study site personnel). At-home subject-verified follow-ups will be conducted via the *REDCap Cloud* online portal accessible by computer, tablet, or smartphone.

The following activities will be completed at the Baseline Visit.

- The subject will receive an explanation of the study purpose and procedures, sign the electronic informed consent form (eICF), physician will review eligibility check list, if female of child-bearing potential, subject will complete a urine pregnancy test.
- Together, physician and subject will create an account on *REDCap Cloud*.
- Together, physician and subject will complete the baseline assessment measuring:
 - Demographics;
 - Chronic pain classification;
 - Cannabis experience;
 - Concomitant medications;
 - Treatment goal;
 - ST treatment regimen;
 - Brief Pain Inventory-Short Form (BPI-SF);
 - Euro Quality of Life Assessment (EQ5D-5L).
- The subject will be scheduled for the first physician-verified follow-up visit approximately 2 months after the initiation of treatment with an ST product.

The following activities will be completed at each physician-verified follow-up visit:

- Physician and subject will discuss the overall treatment regimen.
- Physician will review the subject's online *REDCap Cloud* entries.
- Together, physician and subject will complete the follow-up visit assessment measuring:
 - ST treatment regimen
 - Concomitant medications
 - Clinician Global Impression of Improvement (CGI-I)
 - BPI-SF
 - EQ5D-5L
 - Patient Global Impression of Change (PGI-C)
 - Physician adverse events (AEs) form

The following measures are to be completed by the subject for each at-home follow-up:

- ST treatment regimen
- Additional cannabis consumption
- BPI-SF
- EQ5D-5L
- Patient Global Impression of Change (PGI-C)
- Subject adverse events (AEs) log

In the event of ST treatment discontinuation or study dropout, physicians will be asked to attempt to follow-up with subjects for the completion of the ST Discontinuation assessment and Exit assessment. Based on physician answers to the ST Discontinuation Assessment, subjects will either stay enrolled in the study (e.g., discontinue all cannabis treatment, but continue to be monitor by site physician for chronic pain), or be withdrawn (e.g., unwilling to stay in the study, switched cannabis licensed producer).

A complete schedule of events is provided in **Table 1**.

Safety Monitoring:

Spontaneous AE reporting will be entered in *REDCap Cloud* by the subject during subject follow-ups, using the Subject AE log. Physicians will verify and assess all AEs entered at physician follow-ups, using the Physician AEs form. All serious adverse events will be sent directly to Canopy Growth's Global Pharmacovigilance Department (GPVD) in real-time, where they will be reviewed with respect to country specific regulatory requirements. All non-serious adverse events will be sent in a monthly report to GPVD.

Outcome Assessments:

- The BPI-SF is a 9-item self-report questionnaire that includes 6 pain items (e.g., location, 24-hour worst pain, 24-hour average pain, pain right now); 2 treatment items; and 1 (7 part) pain interference item.
- EQ5D-5L is a 5-category questionnaire (total of 6 questions) assessing mobility, self-care, usual activities, pain/discomfort, anxiety/depression, and overall health on a scale from 0-100 (where 100 denotes the best, and 0 the worst health).
- The PGI-C is a 1-item self-report outcome question that measures a subject's overall impression of improvement during treatment using a 7-point Likert-type scale. The PGI-C shows good performance in subjects with chronic pain and is often more responsive than primary measures of pain intensity.
- The CGI-I is a 1-item clinician-reported outcome question, similar to the PGI-C, that measures a clinician's overall impression of subject improvement in response to treatment using a 7-point Likert-type scale. The CGI-I typically correlates well with the PGI-C.

Duration of Subject Participation and Treatment: Subjects will be followed for one year, unless the subject withdraws early, either independently or in response to physician recommendation. ST treatment will continue for as long as subjects and physicians agree that there is a benefit and treatment is tolerated.

Study Population

Subject Inclusion Criteria:

Subjects must meet all of the following criteria to be eligible for enrollment into the study:

1. Subject \geq 25 years of age with a diagnosis of chronic non-cancer pain defined as pain lasting or recurring over a period $>$ 3 months (IASP-ICD-11 classification, refer to Appendix 6).
2. Subject is, in the physician's opinion, a candidate for medical cannabis treatment. Candidate status will be determined based on local regulations, common clinical practice, available guidelines and scientific literature, and the physician's expertise or experience with medical cannabis products.
3. Subject received a prescription/authorization for a product in the medical channel of Spectrum Therapeutics.
4. Subject is able to read and understand the informed consent form and complete the study questionnaires.

Subject Exclusion Criteria:

Subjects meeting any of the following criteria will not be eligible for participation in the study:

1. Subject refuses to provide informed consent or participate in any aspect of the study.
2. Subject is pregnant or lactating.
3. Subject has a history of psychosis or schizophrenia (or other significant psychiatric disorder), including among first-degree relatives.
4. Subject has a suspected or confirmed cardiovascular disease.
5. Subject is a liver transplant recipient or has severely compromised liver function.

Endpoints:

Primary endpoints

- Physician selection of Spectrum Therapeutics (ST) medical cannabis treatment regimen and changes over time in:
 - (1) average daily dose of THC and CBD (in mg);
 - (2) route of administration (inhaled or ingested).

Secondary endpoints

- Subject selection of ST treatment regimen and changes over time in:
 - (1) average daily dose of THC and CBD (in mg);
 - (2) route of administration (inhaled or ingested).
- Change in BPI-SF responses from baseline.
- Change in EQ5D-5L responses from baseline.
- PGI-C for the target treatment goal.
- CGI-I for the target treatment goal.
- In subjects taking an opioid, changes in opioid use over time (calculated as milligram morphine equivalents [MME]/day).
- Among subjects taking other medication, total daily dose change over time.

Safety endpoint

- Incidence of AEs stratified by product and formulation.

Statistical Methods:

The Sponsor will perform statistical analyses. The Sponsor or designee will extract and analyze descriptive data every 6 months. This will be done to keep sites apprised of study progress. A de-identified summary report will be generated and delivered to all registered site physicians.

The report will indicate:

- The number of physician-collaborators stratified by country.
- The number of subjects enrolled stratified by country.
- Subject demographics, chronic pain classification, and treatment goal.
- Subject concomitant medication use.
- Subject ST treatment regimens.
- Incidence of AEs per individual ST product.

Upon database lock a series of analysis will be conducted to address study objectives. For each analysis, the normality of the data distributions will be ascertained using the Shapiro-Wilk test of normality and Levene's test of equality of error variance. Descriptive statistics (frequencies, means, and standard deviations for normally distributed parametric data; medians and interquartile ranges for nonparametric data) will be used to characterize the sample. Outcome analyses will include a change in ST regimen; a change in reported opioid consumption in MME/day; change in daily dose of other medications, including analgesics, sedatives, and benzodiazepines; change in responses to BPI-SF items and EQ-5DL items; initial PGI-C and changes over time; and initial CGI-I and changes over time. For the safety endpoint, AEs will be tabulated descriptively. Detailed analyses are outlined in the Statistical Analysis Plan.

Number of Subjects (Planned):

Given a continuous enrollment design, the study will include two enrollment milestones over the 2-year study period. Milestone 1, targeted for the end of year 1 will be to recruit 750 subjects. Milestone 2, targeted for the end of year 2 will be to recruit 750 subjects. To enroll a total of up to 1500 subjects. The number of subjects may vary based on the real-life use of ST products. Sites will be recruited from countries where ST products are available: Canada, United Kingdom, Germany, and Australia. Sites from additional countries may be included as ST products are rolled out in those countries and based on site feasibility.

The present study has an observational design that poses low-burden for subjects, as the number and frequency of in-clinic (telemedicine) visits represent those necessary for adequate monitoring of treatment for chronic pain and at-home follow-ups will be completed using a simple online app and take no longer than 15 minutes to complete. On this premise, we did not restrict the sample size based on an estimated minimum required sample. Furthermore, the observational nature of the primary endpoint (daily average dose [in mg] of THC and CBD and mode of administration [inhaled or ingested]), did not permit an a priori power analysis to estimate sample size. A sample size of 1500 subjects is consistent with similar previous observational registry studies.

Table 1. Schedule of Events

	Day 1	Month 1 (+/-7d)	Month 2 (+/-7d)	Month 3 (+/-7d)	Month 4 (+/-7d)	Month 6 (+/-7d)	Month 8 (+/-7d)	Month 10 (+/-7d)	Month 12 (+/-7d)	Un-scheduled visit
	Physician Baseline Visit	Subject-verified Follow-up 1	Physician Follow-up 1	Subject-verified Follow-up 2	Physician Follow-up 2	Subject-verified Follow-up 3	Physician Follow-up 3	Subject-verified Follow-up 4	Physician Follow-up 4	
Electronic Informed consent form (eICF)	X									
Pregnancy Test	X									
Review eligibility criteria check list	X									
Create subject REDCap Cloud account	X									
Demographics	X									
Concomitant medications	X		X		X		X		X	X
Chronic Pain Classification	X									
Cannabis experience	X									
Treatment goal	X									
ST treatment regimen	X	X	X	X	X	X	X	X	X	X
Additional cannabis consumption		X		X		X		X		
BPI-SF ¹	X	X	X	X	X	X	X	X	X	X
EQ5D-5L ²	X	X	X	X	X	X	X	X	X	X
PGI-C		X	X	X	X	X	X	X	X	X
CGI-I			X		X		X		X	X
Subject AE ³ log		X		X		X		X		
Physician AE ³ form			X		X		X		X	X
ST discontinuation assessment										X
Exit assessment										X

Abbreviations: AE, adverse event; BPI-SF, Brief Pain Inventory-Short Form; CGI-I, Clinical Global Impression-Improvement; PGI-C, Patient-Global Impression of Change; eICF, electronic informed consent form; EQ5D-5L-European QoL; ST, Spectrum Therapeutics.

¹. The subject-verified visits will only include numeric rating scale pain items from the BPI.

². EQ5D-5L- QoL (5 category questionnaires to be completed by the subject)

³. AEs recorded by the subject at subject-verified follow-ups will be assessed by the physician at physician verified follow-up.

ABBREVIATIONS AND DEFINITIONS OF TERMS

Abbreviation/Term	Definition
AE	Adverse event
BMI	Body mass index
BPI-SF	Brief Pain Inventory-Short Form
CBD	Cannabidiol
CGI-I	Clinician Global Impression-Improvement
eCRF	Electronic case report form
ECS	Endocannabinoid system
eICF	Electronic informed consent form
EQ5D-5L	Euro Quality of Life (QoL)
GCP	Good Clinical Practice
GPVD	Global Pharmacovigilance Department
IASP	International Association for the Study of Pain
ICF	Informed consent form
ICH	International Council for Harmonization
IME	Important Medical Event List
MME	Milligram morphine equivalents
MSL	Medical science liaison
NRS	Numeric rating scale
PGI-C	Patient Global Impression of Change
SAE	Serious adverse event
SD	Standard deviation
ST	Spectrum Therapeutics

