At the first visit (Day 1), subjects will complete the informed consent. A pregnancy test will be administered to women of childbearing potential, and the site physician or study site personnel will confirm subject eligibility criteria. Following this, the site physician or study site personnel trained in the use of *REDCap Cloud* will assist each subject in creating a *REDCap Cloud* account and completing the baseline assessment (Appendix 1). The first visit (Day 1) will assess important baseline information, including demographics, chronic pain classification, cannabis experience, concomitant medications, treatment goal, and ST treatment regimen. Subjects will complete the Brief Pain Inventory-Short Form (BPI-SF) and Euro- Quality of life Assessment (EQ5DL) at this visit.

At each subsequent physician-verified visit (a total of 4), the site physician or study site personnel will assist with the completion of physician follow-up assessment (Appendix 2) via *REDCap Cloud*, and reassess ST treatment regimen, concomitant medications, effectiveness and tolerability of the ST treatment regimen (including AEs & SAEs). Subjects will complete the BPI-SF, EQ5DL, and Patient Global Impression of Change (PGI-C) and physicians will complete the Clinical Global Impression-Improvement (CGI-I).

Four subject-verified follow-up assessments will be completed by subjects via the *REDCap Cloud* online portal (Appendix 3). Subjects will receive an automated email one week prior and the day of subject-verified follow-up with a reminder to complete the online assessment. The subject-verified online assessment will include questions about their ST treatment regimen, additional cannabis consumption, numeric rating scale (NRS) pain items of the BPI-SF, the EQ5D-5L, and the PGI-C.

Spontaneous AE reporting will be entered in *REDCap Cloud* by the subject during subject follow-up assessments, using the Subject AE log (Appendix 3). Physicians will verify and assess all AEs entered at physician follow-ups, using the Physician AE form (Appendix 2). All serious adverse events will be sent directly to Canopy Growth's Global Pharmacovigilance Department (GPVD) in real-time, where they will be reviewed with respect to country specific regulatory requirements. All non-serious adverse events will be sent in a monthly report to GPVD.

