7.2.7 AEs/SAEs

All enrolled subjects and site physicians will receive guidance on AE reporting during the investigator training. Spontaneous AE reporting will be entered in *REDCap Cloud* by the subject, during at-home follow-up (subject to verification by physician at physician-verified follow-up). Physicians will classify each AE by seriousness, severity and inferred relation to the study product in the Physician AE form as described below. The GPVD will also review all SAEs with respect to applicable regulatory requirements.

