8.2 Data Management

The *REDCap Cloud* system uses a variety of mechanisms for checking data at the time of entry including skip logic, range checks, and data type checks. Upon receipt of new data, the personnel at the Methods Center will query all missing, implausible, or inconsistent data. Study site personnel will be able to conduct a review of open queries in the system and will be trained/required to respond promptly.

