8.3 Data Monitoring

Data will be monitored by the Sponsor consistent with International Council for Harmonization (ICH) Good Clinical Practice (GCP) guidelines. Source data verification will be performed remotely on 10% of study sites. Continuous, real-time monitoring of data quality and completeness will be performed remotely by the Sponsor. The registry project management team will periodically review site compliance (completion of scheduled visits and questionnaires), send reminders for missed at-home subject follow-up questionnaires, and guarantee that all efforts are made to contact subjects who discontinue the study or ST treatment prior to 1-year follow-up. Issues with data quality or completeness will be addressed on a case-by-case basis and, if necessary, brought to the attention of the Sponsor when requiring remedial action (e.g., retraining of a site).

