Onset date of event

(YYYY-MM-DD)

End date of event

(YYYY-MM-DD)

Select seriousness criteria

- Non-serious
- Death
- Life-Threatening
- Inpatient/Prolonged Hospitalization
- Congenital Anomaly/Birth Defect
- Persistent of Significant Disability /Incapacity
- Other Medically Important Condition

Admission date

(YYYY-MM-DD)

Discharge date

(YYYY-MM-DD)

Date of death

(YYYY-MM-DD)

Cause of death

Was an autopsy performed?

- Yes
- No

Please provide autopsy results

Select outcome of event(s)

- Recovered
- Recovering
- Ongoing
- Fatal
- Unknown

Select severity

- Mild
- Moderate
- Severe

Investigator Causality Assessment:

- Related
- Probable
- Possible
- Unlikely
- Not related

Please describe alternate possible causes for the AE?

Please provide patients medical history

Please provide a summary of the patients course during the time of the event (AE, symptoms, events chronology, treatments, medical history, titration information, outcome per event, etc.).

CGI-I

Clinician Global Impression of Improvement

Since the start of Spectrum Therapeutics treatment, my patient's overall symptom status is:

(best describe how your patient's symptom is now, compared with how it was before they began taking medical cannabis)

- Very Much Improved -nearly all better; good level of functioning; minimal symptoms; represents a very substantial change
- Much Improved -notably better with significant reduction of symptoms; increase in the level of functioning but some symptoms remain
- Minimally Improved -slightly better with little or no clinically meaningful reduction of symptoms. Represents very little change in basic clinical status, level of care, or functional capacity
- No Change -symptoms remain essentially unchanged
- Minimally Worse -slightly worse but may not be clinically meaningful; may represent very little change in basic clinical status or functional capacity
- Much Worse -clinically significant increase in symptoms and diminished functioning
- Very Much Worse -severe exacerbation of symptoms and loss of functioning

Patient reported outcomes

BPI

Throughout our lives, most of us have had pain from time to time (such as minor headaches, sprains, and toothaches). Have you had pain other than these everyday kinds of pain today?

- Yes
- No

Please select the number (0= no pain, 10= pain as bad as you can imagine) that best describes your pain at its worst in the last 24 hours.

- 0
- 1
- 2
- 3
- 4
- 5
- 6
- 7
- 8
- 9
- 10

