[Branching logic exists]

If known, please provide the temperature set point of your patient's vaporizer (in °C) _____

(inhal_vape_temp)
(125 / 300)
[Branching logic exists]

Calculated, approximated total daily dose of THC and CBD (in mgs)		
	THC	CBD
Inhaled	(inhal_THC)  View Equation	(inhal_CBD)  View Equation
Ingested	(ingest_THC)  View Equation	(ingest_CBD)  View Equation

Side Effects

Does your daily dose include any side effects (e.g. nausea, dry mouth, drowsiness, euphoria, etc.)?

- Yes
- No

You indicated that you experience side effects from your daily dose. Please indicate which side effects you experience (check all that apply)

- Nausea
- Dry Mouth
- Dizziness
- Somnolence (i.e. sleepiness/drowsiness)
- Euphoria
- Other

Please describe the 'other' side effects that you experienced

Subject Adverse Event Reporting

AE diary

Since you have been taking Spectrum Therapeutics medical cannabis products, have you experienced any side effects? Please include any side effects you have experienced, regardless of whether you believe they are related to medical cannabis.

- Yes
- No

Please describe in as much detail the adverse event (side effect) that you experienced.

Adverse events, symptoms, start date/end date, event(s) chronology, treatments, outcome.

PGI-C

Global Impression of Change

Since the start of Spectrum Therapeutics treatment, my overall symptom status is:

(best describe how your symptom is now, compared with how it was before you began taking medical cannabis)

- Very Much Improved
- Much Improved
- Minimally Improved
- No Change
- Minimally Worse
- Much Worse
- Very Much Worse

Patient reported outcomes

BPI

Throughout our lives, most of us have had pain from time to time (such as minor headaches, sprains, and toothaches). Have you had pain other than these everyday kinds of pain today?

- Yes
- No

Please select the number (0= no pain, 10= pain as bad as you can imagine) that best describes your pain at its worst in the last 24 hours.

- 0
- 1
- 2
- 3
- 4
- 5
- 6
- 7
- 8
- 9
- 10

Please select the number (0= no pain, 10= pain as bad as you can imagine) that best describes your pain at its least in the last 24 hours.

- 0
- 1
- 2
- 3
- 4
- 5
- 6
- 7
- 8
- 9
- 10

Please select the number (0= no pain, 10= pain as bad as you can imagine) that best describes your pain on the average.

- 0
- 1
- 2
- 3
- 4
- 5
- 6
- 7
- 8
- 9

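### Real-time SAE reporting is not assured for events subjects enter at home, because their seriousness is next due to be classed at a physician follow-up 1 or 2 months later

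*Protocol*

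**What the plan says.** The synopsis (Safety Monitoring) and section 3.1 send every SAE directly to the sponsor's Global Pharmacovigilance "Department (GPVD) in real-time, where they will be reviewed with respect to country specific regulatory requirements". Non-serious events go to the same department in a monthly report.

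For events entered by subjects, assessment is placed at the physician's follow-up. Table 1 footnote 3: "AEs recorded by the subject at subject-verified follow-ups will be assessed by the physician at physician verified follow-up". The synopsis: "Physicians will verify and assess all AEs entered at physician follow-ups, using the Physician AEs form". Section 7.2.7 gives the classification to the physician: "Physicians will classify each AE by seriousness, severity and inferred relation to the study product in the Physician AE form". Table 1 schedules that form at months 2, 4, 8 and 12 and at unscheduled visits. It schedules the Subject AE log at months 1, 3, 6 and 10.

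The two forms differ. The Physician AE form (Appendix 2) has a field headed "Select seriousness criteria". The Subject AE log (Appendix 3) has one yes/no question and a free-text box with the prompt "Adverse events, symptoms, start date/end date, event(s) chronology, treatments, outcome". It has no seriousness item.

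**The concern.** An event cannot be sent as an SAE until someone has recognised it as serious. For an event first recorded at home, the only scheduled step that does this is the next physician-verified follow-up. A subject could describe a hospital stay in the free text, and nothing in the protocol would require anyone to read that entry for safety before the visit.

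What is at stake is the timeliness of safety surveillance. GPVD's review against each country's requirements could begin weeks after the information was already in the database. Safety and tolerability is a stated objective (section 2.1.3), and four of the eight scheduled post-baseline contacts are at-home entries. A reader of the real-time sentence would expect closer surveillance of these events than the described process delivers.

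**Working it through.** **Inputs.** Table 1 gives subject follow-ups at months 1, 3, 6 and 10 and physician follow-ups at months 2, 4, 8 and 12, each with a window of ±7 days. The protocol states no lag of its own, so there is no figure to reproduce.

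**Formula.** Nominal lag = month of the next physician follow-up − month of the at-home entry. One month is taken as 365.25 / 12 = 30.4 days. Each end of the interval can move by 7 days, so the range is the nominal lag ± 14 days.

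| At-home entry | Next physician follow-up | Nominal lag | Range |
|---|---|---|---|
| Month 1 | Month 2 | 1 month (30.4 days) | 30.4 − 14 = 16.4 to 30.4 + 14 = 44.4 days |
| Month 3 | Month 4 | 1 month (30.4 days) | 16.4 to 44.4 days |
| Month 6 | Month 8 | 2 months (60.8 days) | 60.8 − 14 = 46.8 to 60.8 + 14 = 74.8 days |
| Month 10 | Month 12 | 2 months (60.8 days) | 46.8 to 74.8 days |

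These lags run from entry, not from onset. A missed physician visit lengthens them: an entry at month 3 with the month 4 visit missed would wait until month 8, which is 8 − 3 = 5 months.

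**Does another provision in the protocol guarantee an earlier look?**

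- *Unscheduled visits* (section 3.1, Table 1). The Physician AE form may be used there, but the visit depends on the physician's judgement and is not tied to a subject's entry.
- *Company judgement* (section 7.2.7.2). The company may deem an event serious, but no step has it read subject entries for safety.
- *Data queries* (section 8.2): "the personnel at the Methods Center will query all missing, implausible, or inconsistent data". A clear and complete account of a hospital stay is none of these.
- *Sponsor monitoring* (section 8.3): "Continuous, real-time monitoring of data quality and completeness will be performed remotely by the Sponsor". Its stated scope is not safety triage.
- *GPVD review* (section 7.2.7). It covers SAEs, so it follows classification.
- *Monthly report* (synopsis, section 3.1). It is stated for non-serious events. Nothing says whether entries not yet classed are included.

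Some of these could bring an event to light early. None is triggered by an at-home entry.

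**The case against.** The strongest reply is that nothing here is stated wrongly. The real-time sentence concerns serious events, an event becomes serious when the physician classes it, and footnote 3 and the real-time sentence then describe successive steps. That reading is natural, and on it there is no literal contradiction. But the protocol never says when the clock starts, and the wait between entry and classification is the same on either reading.

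The second reply is that the finding rests on silence. Section 7.2.7 promises guidance on AE reporting to subjects and physicians, section 5.2 includes safety training, and sections 8.4 and 8.5 give site physicians access to their own subjects' data. Subject-facing instructions could also sit in consent or contact pages that are not available here, or in a separate safety plan. This is fair as far as it goes: the content of the guidance is unknown, so one cannot say that subjects are not told to call the site. But access is not a duty to review, and the protocol neither describes nor cites a triage step. If unclassed entries do go into the monthly report, GPVD could see them within about a month and the 2-month figures would overstate the delay to GPVD, but the text does not say so, and a monthly report is not real time.

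Three limits stand. The lag matters only for serious events first recorded in the at-home log, and the protocol gives no basis for estimating how many there would be. Later classification does not change the planned safety endpoint, the descriptive incidence of AEs by product and formulation. Finally, the synopsis counts the first physician follow-up from the start of treatment while Table 1 counts from Day 1, so the first interval may differ somewhat from the range shown.

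**Conclusion.** The concern holds and should be fixed. Followed as written, the protocol leaves the seriousness of an at-home entry unclassed for nominally 1 month (about 16–44 days) after months 1 and 3 and 2 months (about 47–75 days) after months 6 and 10, unless an unscheduled visit or other contact comes first. This assumes the Table 1 calendar and windows, attendance at the next physician follow-up, and no triage procedure outside the protocol. SAEs that the physician or company learns of by another route are unaffected. The weakness lies in the timeliness of safety reporting and not in the effect estimates.

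**What to change.** Add to the Subject AE log, as yes/no items, the outcomes in section 7.2.7.2 that a subject can report: a life-threatening event, hospitalisation or a prolonged stay, disability or incapacity, and a congenital anomaly or birth defect. Model them on the existing field in the Physician AE form. Let any yes send an automatic REDCap Cloud alert to the site physician and GPVD, with seriousness classed in response to the alert and not left to the next visit. State when the real-time clock starts, and say how subject entries not yet classed are handled in the monthly report. Bring footnote 3, the synopsis safety paragraph, section 3.1 and section 7.2.7 into line.

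The cost is four form items, one alert in a system that already sends automated emails, and matching wording in four places. Someone must answer the alerts, some of which will prove non-serious, and the protocol gives no figure from which to estimate that load. The four items will not catch every medically important event. Those they miss would still depend on the physician's reading of the free text.
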